6.2.4 Treatment assignment, randomization

After meeting all inclusion/exclusion criteria and obtaining informed consent, patients will be randomized using a 1:1 allocation ratio to one of the two study arms. Randomization will be centralized through REDcap Cloud at C5 research at the Cleveland Clinic. Randomization will be stratified by site.

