10.3 Analysis of the primary and secondary endpoints

Based on preliminary case-control data of patients with severe COVID-19 pneumonia treated with mavrilimumab, we estimate that 40% of patients in the placebo group will meet the primary endpoint compared to 80% of treated patients. A sample size of 30 patients per arm (60 total) will provide at least 80% power to detect this difference using a 2-sided alpha of 0.05.

The results of our study will inform treatment effect to aid in the planning of larger studies. The primary efficacy analysis will be on an intention-to-treat basis and include all patients who are randomized. Use of supplemental oxygen and vital status will be assessed daily up to day 14. Patients will be considered to have met the primary endpoint if the patient is alive at day 14 and has not used supplemental oxygen for at least 24 hours, regardless of whether or not the patient is still in the hospital (i.e. success=1). All other patients will be counted as not meeting the primary endpoint (i.e. success=0), including deaths on or before day 14 and patients for whom information cannot be ascertained (eg.lost to follow-up, withdrew consent, or otherwise missing information on the primary endpoint at day 14). This is analogous to imputing the worst case scenario for missing data.

The primary analysis will report the number and percentage of patients meeting the primary endpoint. The chi-square statistic will be used to test the difference between the two treatment groups. The time to freedom from supplemental oxygen will also be displayed geographically with a Kaplan Meier curve. A two-sided p value of < 0.049 will be considered statistically significant for the primary endpoint, though as noted, an important aspect of this study is to better define the magnitude of the treatment effect of our clinical outcomes to appropriately power larger studies.

The secondary endpoints are the proportion of patients alive at day 28 (i.e. success=1), and the proportion of patients alive and without respiratory failure at day 28 (i.e. success=1). Similar to the primary analysis, patients not meeting the this criteria in each of the secondary endpoints will be considered a failure (i.e. success=0), including deaths on or before day 28 and patients

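### Randomisation is stratified by site but the primary chi-square ignores site: the test is valid and adequately powered, but conservative if sites differ in outcome

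*Combined protocol and SAP*

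**What the plan says.** **Randomisation (Section 6.2.4).** Allocation is central: "patients will be randomized using a 1:1 allocation ratio to one of the two study arms". Then: "Randomization will be stratified by site". Site is the only stratification factor. The number of sites and the block size are not given.

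**Primary test (Section 10.3).** "The chi-square statistic will be used to test the difference between the two treatment groups". The success criterion is: "A two-sided p value of < 0.049 will be considered statistically significant for the primary endpoint". No stratified test, site-adjusted model or sensitivity analysis by site is specified. In the analysis chapter, site appears only in Section 10.2, as a descriptive count of enrolment.

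**Sample size (Section 10.3).** The planning rates are given as follows: "we estimate that 40% of patients in the placebo group will meet the primary endpoint compared to 80% of treated patients". The power claim that rests on them is: "A sample size of 30 patients per arm (60 total) will provide at least 80% power to detect this difference". The alpha for that calculation is 0.05, two-sided.

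**Day-28 secondary endpoints (Section 10.3).** These are presented as point estimates with 95% confidence intervals, without multiplicity adjustment. No significance threshold or power is attached to them.

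**The concern.** Blocking within site balances the arms inside each site, so differences between sites largely cancel out of the treatment comparison. The pooled 2x2 chi-square does not use this. Its variance is computed as if all 60 patients came from one population, so between-site variation is counted as noise. When sites differ in outcome, the statistic is therefore too small on average, its actual type I error falls below 0.049, and some power is given up.

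The 40-point planning effect comes from preliminary case-control data, so a smaller true effect is a realistic possibility, and there a few points of power count for more. The plan also wants the result to inform whether a larger study follows. If the choice between a stratified and an unstratified test is left open until the data are seen, the two could fall on opposite sides of 0.049.

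**Working it through.** **1. The plan's own figure.** Inputs from Section 10.3: 30 per arm, 40% against 80%, two-sided 0.05. The pooled rate is 0.60.
- Null standard error: sqrt(2 × 0.6 × 0.4 / 30) = 0.1265.
- Alternative standard error: sqrt(0.4 × 0.6 / 30 + 0.8 × 0.2 / 30) = 0.1155.
- Power = Φ[(0.40 − 1.960 × 0.1265) / 0.1155] = Φ(1.317) = 90.6%.

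At 0.049 the same formula gives 90.4%, so the difference between the two alphas is immaterial here. Exact enumeration gives 90.5% for the Pearson chi-square, and 85.1% with a continuity correction or Fisher's test. The stated lower bound of 80% is met in every case.

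**2. Why the pooled test is conservative.** With exact balance within equal-sized sites and no treatment effect, the variance of the treatment difference is proportional to the mean of p_s(1 − p_s) over sites. The pooled chi-square uses p̄(1 − p̄), which equals that mean plus Var(p_s).

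As an illustration, let half the sites have a 18% success rate and half 62%. These are the rates at ±1 SD when the between-site logit SD is 1.0 and the overall rate is 40%.
- Pooled: 0.40 × 0.60 = 0.240.
- Within site: (0.18 × 0.82 + 0.62 × 0.38) / 2 = 0.1916.
- Ratio: 0.1916 / 0.240 = 0.798.
- The critical value for 0.049 is 1.969; the effective one is 1.969 / sqrt(0.798) = 2.20.
- Actual type I error: 2 × [1 − Φ(2.20)] ≈ 0.028.

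This is an idealised case. With a few sites drawn at random, the realised spread is usually smaller, and incomplete blocks leave some imbalance, so simulated values lie closer to 0.049.

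**3. Simulation.** All of these are assumptions, because the documents give none of them: 60 patients split as 20/20/20, 24/16/12/8, 20/14/10/8/5/3 or 16/12/10/8/6/4/2/2; permuted blocks of 4 within site; random site intercepts on the logit scale; overall rates held fixed; sites under 6 patients pooled into one stratum for CMH. Both tests use p < 0.049.

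| Between-site logit SD | Type I error, chi-square | CMH gain at 80% vs 40% | CMH gain at 70% vs 40% |
|---|---|---|---|
| 0 | about 0.05 | 0 to 1.5 points lost (both effects) | 0 to 1.5 points lost (both effects) |
| 0.5 | 0.044–0.046 | 0.1 to 0.5 points | −0.2 to +0.9 points |
| 1.0 | 0.035–0.04 | about 2 points (0.91–0.92 to 0.93–0.94) | 3 to 4 points (0.67–0.69 to 0.71–0.73) |
| 1.5 | 0.026–0.029 | 3 to 4 points | 8 to 9 points (0.68–0.70 to 0.76–0.78) |

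The type I error of CMH stays at about 0.045 to 0.05 throughout. The 70% rate is an assumption; the plan uses 80%.

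**4. Two checks on the mechanism.**
- Under simple randomisation (five sites of 12), the chi-square's type I error is 0.050 to 0.052 at SD 0 to 1.0. The conservatism therefore comes from the within-site balance.
- With ten unpooled sites of 6 and SD 0, CMH has 89.2% power against 90.7% for the chi-square at 80% against 40%. Sparse strata cost power, so a pooling rule is needed.

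**The case against.** The strongest case against acting is that nothing is broken. The unstratified chi-square is valid, simple and common in small proof-of-concept trials. Its type I error does not rise when sites differ, and its power at the planning effect stays at 0.91 or above. Power is lost only relative to another test. At SD 0.5 the gain is negligible, and the larger gains need a between-site spread that no section of the protocol supports. All of this stands, and it limits the point to efficiency and to matching the analysis to the design.

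Pooling small sites also means that the analysis strata no longer match the randomisation strata exactly, and the cutoff of 6 is a choice, not a derived value. That stands too, but it is a small departure compared with ignoring site altogether.

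Four stronger readings may tempt a reader, and the documents support none of them:
- **That the mismatch inflates type I error or leaves the trial underpowered.** The error moves the other way, and the stated power is exceeded.
- **That site differences are shown to be likely because stopping oxygen follows each site's standard care.** Section 2 leaves the decision to standard care only for patients discharged on oxygen before day 14, and assigns it to the prescribing provider. Hospitalised patients have a common saturation criterion. Site differences are plausible, but their size is unknown.
- **That the same type I error and power loss applies to the Day-28 secondary endpoints.** They are estimated with intervals and not formally tested, so only interval width could be affected.
- **That the chi-square already means a stratified one.** No stratum is mentioned. If CMH was intended, Section 10.3 needs to say so.

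**Conclusion.** The mismatch between Sections 6.2.4 and 10.3 is real, and its direction is certain: if sites differ in outcome, the planned test is conservative. Its size is uncertain. At the planning effect the power given up is under 1 point at a between-site logit SD of 0.5, about 2 points at 1.0 and 3 to 4 points at 1.5. At an assumed 70% against 40% it is about 0 to 1, 3 to 4 and 8 to 9 points. If sites do not differ, the stratified test loses 0 to 1.5 points. These figures rest on the assumed site layouts, blocks of 4 and the pooling rule. This is a worthwhile refinement at almost no cost; it is not a validity error, and the sample size statement stands.

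**What to change.** In Section 10.3:

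1. Make the primary test a Cochran-Mantel-Haenszel test stratified by site, without continuity correction, at the same two-sided 0.049 threshold.
2. State how small sites are pooled, and fix the rule before unblinding. The figures above use one pooled stratum for sites with fewer than 6 randomised patients.
3. Report the site-stratified risk difference with a confidence interval. The plan's stated interest is the magnitude of the effect, and a change of test alone does not serve that.
4. Keep the unstratified chi-square as a sensitivity analysis.
5. For the two Day-28 secondary endpoints, use the same strata for the confidence interval only.

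The cost is a short paragraph of analysis text. No patients or data are added, because site is already recorded for randomisation. The downside is a power loss of 0 to 1.5 points if sites turn out not to differ; it could reach about 3 points with eight unpooled sites, which is why the pooling rule belongs in the text.

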1.2 Purpose

The purpose of this prospective, proof-of-concept Phase 2, multicenter, blinded, randomized placebo controlled study is to demonstrate that early treatment with mavrilimumab prevents progression of respiratory failure in patients with severe COVID-19 pneumonia and clinical and biological features of hyper-inflammation. These results will lead to and inform a Phase III randomized placebo-controlled trial.

2 Objectives and endpoints

Primary Objective

To demonstrate that early treatment with mavrilimumab prevents progression of respiratory failure in patients with severe COVID-19 pneumonia and clinical and biological features of hyper-inflammation.

Secondary Objectives

- To evaluate mortality
- To evaluate the duration of hospitalization
- To evaluate safety of mavrilimumab

Primary Endpoint

The primary endpoint is the proportion of subjects alive and off of oxygen at day 14.

When hospitalized patients are off of oxygen, this will be documented as an oxygen saturation >90% for at least 5 minutes at rest. For patients that are discharged before day 14, a telehealth visit will be performed at day 14. For patients discharged **off** of oxygen before day 14, the day 14 visit will assess that they are off of oxygen. For patients who are discharged **on** oxygen before day 14, the decision to discontinue oxygen will be based on standard clinical care according to the health provider who prescribed oxygen therapy. The day 14 telehealth visit will assess whether the patient remains on oxygen, and “off of oxygen” will be defined as no supplemental oxygen use for at least the previous 24 hours.

Secondary Endpoints

The secondary end-points are alive at day 28, and the proportion of subjects alive and without respiratory failure at 28 days. Respiratory failure is defined as needing mechanical ventilation, non-invasive ventilation, or high-flow oxygen.

Exploratory Endpoints

- Mortality at day 14
- Mortality at day 60
- Proportion of patients in each category according to the following ordinal scale at day 7, 14, 21, and 28:
 1. Not hospitalized
 2. Hospitalized, no supplemental oxygen
 3. Hospitalized, on supplemental oxygen
 4. Hospitalized, requiring nasal high-flow oxygen or non-invasive ventilation
 5. Hospitalized, requiring ECMO, invasive mechanical ventilation or both
 6. Death
- Freedom from mechanical ventilation
- Duration of hospitalization
- Change in SOFA score at day 7, day 14, day 21, and day 28, or until discharge

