Assessment for “respiratory failure” as defined for the secondary endpoint														X
Assessment of survival (day of death if occurs) ^m	X											X	X	
Mavrilimumab/placebo administration		X												

^a Given resource limitation related to COVID-19, all laboratory testing is considered standard of care, though as possible, certain tests that are not considered standard of care may be obtained for research. If the laboratory tests in the schedule of activities are obtained, they will be documented accordingly. If laboratory tests cannot be obtained for other reasons, such as requiring extra use of personal protective equipment, unnecessary exposure to healthcare personnel, or safety issues related to obtaining and processing samples, these will not be considered a protocol deviation.

^b Study visits are planned for hospitalized patients only; planned activities that fall on study days that occur after the patient is discharged will not be done.

^c Screening activities can occur from -3 and 0 days before enrollment except for 2019-nCoV testing, which can occur between -7 and 0 days before enrollment.

^d For hospitalized patients, this visit will include the activities listed. For patients who have been discharged before Study Day 28, this visit will be conducted by phone/telehealth but will not include any laboratory tests.

^d An unscheduled visit is planned to occur on the day of discharge if the patient is discharged before Day 28; in which case this will serve as an early termination visit. If patient is discharged the visit on Study Day 28±3 and Study Day 60±3, will be done by telephone call follow-up and lab tests will not be performed. May also be used for adverse event assessments.

* Nasopharyngeal or oropharyngeal swabs for SARS-CoV2 RNA levels will be performed until negative or discharge. Sampling will include both nostrils, or repeat sampling will include the same nostril if only one nostril is used. A local sample will be used for inclusion criteria, and as possible appreciating the concerns related to extra use of personal protective equipment and exposure to healthcare personnel

"For the purposes of the primary end-point and time to freedom from supplemental oxygen, the ordinal scale and presence of supplemental oxygen will be assessed daily thru Day 14 while hospitalized. If patient has been discharged prior to Day 14, it will be assessed on Day 14, 21 and 28.

^e Collect at least baseline and at least weekly thereafter.

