^g Includes FiO₂, SpO₂, Respiratory rate, note if ventilated or not, if yes collect PEEP; rescue therapy used (e.g., Flolan, proning, NM blockade, ECMO). For FiO₂, SpO₂, and PEEP, best and worst of daily value. Calculate P to F ratio best and worst for each day.

^h Done at Investigator's discretion; not expected to be used for decision to treat; not a mandatory test.

ⁱ Females of child-bearing potential only, urine or serum at investigator's discretion.

^j Includes complete blood count (CBC) and differential at screening and CBC on subsequent indicated days.

^l Prohibited medications include any cell-depleting biological therapies (e.g., anti-CD20) within 12 months prior to Day 0; or previous treatment with noncell-depleting biological therapies (such as anti-tumor necrosis factor [TNF], anakinra, anti-Interleukin [IL]-6 receptor [e.g. tocilizumab], or abatacept) within 8 weeks (or 5 half-lives, whichever is longer) prior to Screening, treatment with alkylating agents within 12 weeks prior to Screening, intramuscular, receipt of live (attenuated) vaccine within the 4 weeks before Day 0, treatment with cyclosporine A, azathioprine, cyclophosphamide, or mycophenolate mofetil (MMF) within 4 weeks of Screening. **Concomitant medications to track include: antipyretics, antibiotics related to secondary infections, and all investigational off-label therapies for COVID-19 for each subject (e.g. chloroquine, hydroxychloroquine, anti-IL-6, corticosteroids, remdesivir, lopinavir/ritonavir) along with time, dose, and duration of their administration.** Other concomitant medications will be recorded at baseline and daily thereafter while hospitalized until Day 7, at Day 14, Day 21 and Day 28. This information will be included in the final study report.

^o Assessed daily thru Day 14 if hospitalized. If the patient is discharged, assess at Day 14.

^m Document whether death occurred after withdrawal of care, and if so, reason for withdrawal of care.

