for whom information cannot be ascertained (e.g. lost to follow-up, withdrew consent, or otherwise missing information on the secondary endpoint at day 28). This is analogous to imputing the worst case scenario for missing data.

The probability of patients achieving the secondary endpoint successfully will also be estimated using Kaplan-Meier estimates and displayed with survival curves. In addition, we do not plan to adjust for multiple hypothesis testing in our secondary and exploratory endpoints. Therefore, these results will be displayed as point estimates with 95% confidence intervals. These intervals should not be regarded as definitive for treatment effects. Finally, we plan to analyze the comparison between mavrilimumab 6 mg/kg versus placebo after all patients have reached day 14 (or have died or been discharged prior to day 14) to expeditiously inform whether a larger study should be undertaken.

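### The Day-14 comparison may start once patients are discharged, but discharge, unlike death, does not settle the Day-14 oxygen endpoint

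*Combined protocol and SAP*

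**What the plan says.** The last paragraph of Section 10.3 plans the comparison of mavrilimumab 6 mg/kg with placebo "after all patients have reached day 14 (or have died or been discharged prior to day 14"), so that a decision on a larger study can be taken quickly. Death and discharge are treated alike as releasing a patient from the wait.

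The same section defines success as being "alive at day 14 and has not used supplemental oxygen for at least 24 hours", whether or not the patient is still in hospital. Deaths on or before Day 14 are failures, as are "patients for whom information cannot be ascertained", with loss to follow-up, withdrawn consent and otherwise missing Day-14 information as the examples.

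Three other places put a discharged patient's assessment at Day 14:

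- Section 2, Primary Endpoint: "For patients that are discharged before day 14, a telehealth visit will be performed at day 14". For patients sent home on oxygen, "The day 14 telehealth visit will assess whether the patient remains on oxygen".
- Table 7-1, footnote on the off-oxygen assessment: "If the patient is discharged, assess at Day 14".
- Table 7-1, note on the primary endpoint: "If patient has been discharged prior to Day 14, it will be assessed on Day 14, 21 and 28".

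**The concern.** The trigger and the endpoint do not match. A patient who goes home on oxygen may stop it by Day 14. One who goes home without oxygen may restart it or die. No section carries discharge status forward to Day 14, and none makes this comparison wait for the telehealth visits. A team that follows the trigger literally could analyse the trial before the endpoint exists for recently enrolled patients who have gone home.

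The direction of any error depends on an unstated choice. If pending patients count as failures, the arm with more early discharges is penalised. If that is mavrilimumab, the estimate moves toward no difference. If early discharge is equal between arms, the mean difference is unbiased. If discharge is instead carried forward as success, the error can favour either arm.

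At stake is the result used to decide whether a larger study follows, in a trial that gives the size of the effect as one of its main purposes.

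**Working it through.** **The rules side by side**

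| Event before Day 14 | Endpoint settled? | Releases the comparison? |
|---|---|---|
| Death | Yes, failure | Yes |
| Discharge | No, set at the Day-14 assessment | Yes |

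**The plan's own power figure.** Inputs from Section 10.3: 30 per arm, 40% v 80%, chi-square test, two-sided 0.05 for sizing and 0.049 for the test.

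Power = Φ{[|p1 − p2|·√n − z·√(2·p̄·q̄)] / √(p1·q1 + p2·q2)}, where p̄ is the mean of p1 and p2
= Φ{[0.4·√30 − 1.960·√0.48] / √0.40} = Φ(1.317) = 90.6%.

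At 0.049 it is 90.4% (exact Pearson 90.5%). The claim of at least 80% is met, and the sample size is not in dispute.

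**How many lost successes would matter.** At the planned counts, 24 v 12 of 30, Pearson χ² = 0.4² / (0.6·0.4·2/30) = 10.0, p = 0.0016. Moving treated successes to failure, with no placebo loss:

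- 4 moved: 20 v 12, p = 0.038, still below 0.049.
- 5 moved: 19 v 12, p = 0.071, above it.

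**How many patients could be pending.** The documents give no discharge times, so these are assumptions:

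- Uniform enrolment over 60 days (Section 3 expects 2 months).
- Early discharge in 25/50%, 35/70% or 40/80% of placebo/mavrilimumab patients, on a day uniform over Days 3 to 14. The excess on mavrilimumab is an input, not a result.
- Early discharges are all eventual Day-14 successes.
- Trigger = the latest, over all 60 patients, of discharge day or Day 14. Data are frozen at the trigger plus a lag. A patient is pending if discharged with Day 14 still ahead at the freeze, and is scored as a failure.

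Results from 40,000 simulated trials per scenario:

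| Early discharge, placebo/mavrilimumab | 25/50% | 35/70% | 40/80% |
|---|---|---|---|
| Mean pending, lag 0: mavrilimumab + placebo | 0.377 + 0.188 | 0.631 + 0.315 | 0.797 + 0.404 |
| Trials with nobody pending, lag 0 | 62% | 48% | 40% |
| Power at 0.049, full data | 90.3% | 90.5% | 90.4% |
| Power at 0.049, lag 0 | 89.2% | 88.4% | 87.6% |
| Conclusion changed, lag 0 | 2.3% | 3.6% | 4.4% |
| Conclusion changed, lag 2 days | 0.5% | 1.0% | 1.1% |
| Conclusion changed, lag 3 days | 0.2% | 0.5% | 0.5% |
| Conclusion changed, lag 7 days | 0.00% | 0.00% | 0.02% |

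The bias follows directly as (pending mavrilimumab − pending placebo)/30. For 25/50% this is (0.377 − 0.188)/30 = 0.6 points. For 35/70% and 40/80% it is 1.1 and 1.3 points, on a planned difference of 40.

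**Sensitivity**

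- Equal early discharge (40/40%): no bias; conclusion changed in 2.2% of trials at lag 0 and 0.5% at 2 days.
- Discharge carried forward as success, with 20% of early discharges failing by Day 14 (25/50% and 35/70%): changed in 0.5% and 1.0% at lag 0, and 0.1% and 0.2% at 2 days.
- Accrual over 30, 90 or 120 days (35/70%, pending = failure): changed in 3.7%, 3.4% or 3.3% at lag 0, and 0.1% or less at 7 days.

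**The case against.** The sentence sets an earliest time, not a data cut, and does not redefine the endpoint. Section 2 and Table 7-1 require the Day-14 contact after discharge, so the natural order is trigger, calls, analysis. Section 9.2 describes site data entry, automatic checks, investigator certification and a database lock, so a freeze at the moment of the trigger is unrealistic. The sentence names no endpoint. Section 10.3 also has a catch-all that scores missing information as failure. Finally, the discharge pattern is assumed, and the bias toward no difference comes from the assumed 2:1 ratio.

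Most of this stands, and it limits the size of the point. A sensible team would probably wait, ordinary data cleaning would remove nearly all of the effect, and an early result could be corrected because Day-14 data are still collected. That the primary endpoint is meant is an inference, though a strong one, since the secondary endpoints fall at Day 28.

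Two things survive. The parenthesis expressly permits not waiting, in a sentence whose stated aim is speed. And the missing-data rule is written for information that cannot be obtained; a call that is not yet due does not clearly fall under it.

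**Conclusion.** The concern holds and is minor. The written trigger conflicts with the plan's own endpoint, because it can be satisfied while the primary outcome of some discharged patients does not yet exist. That conclusion rests on the text alone.

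The size rests on the assumed accrual, discharge times and discharge rates, and on scoring pending patients as failures. Even in the worst case simulated, a mean of 1.20 pending patients is about 3% of the 36 expected successes (24 + 12), and power stays well above the stated 80%. With a week between trigger and freeze the effect is negligible.

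**What to change.** Remove discharge from the parenthesis in Section 10.3. Start the comparison when every randomised patient has either died or reached Day 14 with the Day-14 assessment (telehealth if discharged) completed or documented as unobtainable. Apply the missing-equals-failure rule only at that point.

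As a separate wording point, one Table 7-1 footnote says "planned activities that fall on study days that occur after the patient is discharged will not be done", and the footnote on the discharge visit lists telephone calls only for Day 28 and Day 60. The specific provisions still require the Day-14 contact, but it should be exempted from the first footnote and added to the second.

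Sample size, test and significance threshold are unchanged. In the simulations, waiting for the last patient to reach Day 14 delays the earliest start by 0.5, 0.8 or 1.0 day on average for the three discharge scenarios (95th percentile 2.6, 3.5 or 3.9 days; under 11 days in every run), plus any time needed to complete the calls.
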